In collaboration with our co-investigators at each study site, [name] (Director, VAPAHCS HCV clinic) and [name] (Director, SFVAMC HCV clinic), Veterans (N = 340) diagnosed with liver disease and currently consuming any level of alcohol will be recruited to participate. Drs. [name] and [name] provided estimates of patient flow through each clinic per year and estimates of the percentage of patients reporting any level of alcohol consumption during their visit. Based on these estimates, we anticipate a sufficiently large patient pool from which we may recruit eligible participants. We also estimate, based on national VHA patient demographic data, that approximately 2-5% of clinic patients will be women. We will over sample for women patients in both study clinics utilizing expertise (in recruiting women for research studies) of the Practice Based Research Network (PBRN) based

at Palo Alto (under the leadership of [name], also a consultant) and San Francisco. This will increase our ability to conduct at least exploratory, hypothesis generating sub group analysis in women.

The study sample will be drawn from a population of Veterans who currently receive VA liver clinic services. Veterans presenting to liver clinics who report engaging in any level of alcohol use within the prior 30 days will be recruited for the study. Additional criteria for inclusion include: (a) a liver disorder diagnosis, (b) not presently in treatment for a substance use disorder, and (c) no evidence of active psychosis, dementia, and/or terminal illness. The study will be conducted in liver clinics located at the VAPAHCS and SFVAMC. We estimate that we will need 170 individuals per condition at baseline for a total sample of 340 across both sites, with one half in the experimental condition and TAU condition at each site (i.e., n=85 per condition at Palo Alto, n=85 per condition at San Francisco).

For the formative evaluation, study staff will also perform informal observations of patient flow, and staff and staff-patient relationships in central clinic locations (e.g., nurses' station). Secondly, we will conduct interviews with 10 clinic staff members (5 at each study site) that help us identify possible barriers and facilitators to the sustained adoption of the web-based BAI at both study clinics. The study coordinators will conduct these interviews with providers (N = 10) following the same general recruitment and interview approach as outlined for Aim 1.

Aim 3 (Year 4)

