We estimate that we will need 170 individuals per condition at baseline for a total sample of 340 across both sites, with one half in the experimental condition and TAU condition at each site (i.e., n=85 per condition at Palo Alto, n=85 per condition at San Francisco).

Veterans will be recruited through provider referral, flyers posted in both liver study clinics, and through the use of administrative records (CPRS and CDW) at both sites. The PI and Co-Is will educate providers at each site about the study in their monthly meetings. Study staff will present a brief overview of the study objectives, criteria for Veteran participant eligibility, and low-response options (e.g., contacting study staff within clinic) for referring potential participants to the study. The research team will also provide flyers describing the study (e.g., describing participant eligibility and study team contact information) throughout each of the study clinics. We will place flyers in exam rooms, waiting rooms, and at clinic check-in desks. We will also provide flyers to clinic staff (e.g., nurses and mental health staff) to be given to eligible patients during the exam and subsequent psychosocial assessment.

Finally, in collaboration with our Co-Is, participants will also be recruited through the use of administrative records obtained through CPRS and CDW. Specifically, we plan to identify patients who have completed a scheduled visit during the prior week and mail them a letter (signed by the clinic director for that site) describing the study, eligibility criteria, and a phone number for contacting study staff.

Our research team has extensive experience using these recruitment strategies to good effect. For example, study Co-Principal Investigator [name] is currently conducting an HSR&D funded randomized clinical trial in a VA primary care clinic examining the effect of a web-based BAI on alcohol consumption among Veterans with alcohol misuse. His study is utilizing the above recruitment strategy with excellent results. For example, his [MC] study (n = 160 to date) currently has an 80% recruitment rate among eligible participants, and an 85-90% three- and six-month follow up rate ([name] et al., 2011). We will also take advantage of and utilize recruitment and retention strategies that are well-established among HSR&D investigators at the Center for Health Care Evaluation for use in the present study.

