5.4 Inclusion/Exclusion Criteria

The study sample will be drawn from a population of Veterans who currently receive VA services and providers in two VA Liver Clinics. Veterans presenting to HCV clinics who report engaging in any level of alcohol use within the prior 30 days will be recruited for the study.

Additional criteria for inclusion include: (a) a liver disease diagnosis, (b) not presently in treatment for a substance use disorder, and (c) no evidence of active psychosis, dementia, and/or terminal illness. Any provider responsible for direct patient care at either study site Liver Clinic will be eligible to participate in Aim 1.

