(a) VA Utilization Data. The Office of Mental Health Operations (OMHO) uses the VA National Patient Care Database and the Patient Treatment Files (PTF), and Decision Support System Files (DSS) to characterize quantity and type of SUD and mental health care received by individual VA patients. The OMHO databases include information on number of outpatient visits, residential care received, pharmacotherapy, psychoeducation and psychotherapy receipt, and use of detoxification services. OMHO will provide the project team with utilization data for patients included in the effectiveness study (i.e., Aim 2).

(b) VA Cost Data. Using the DSS, OMHO will provide costs associated with each of the care elements described in the utilization data sets.

(c) Non-VA Care-Utilization and Cost Data (paid for by VA). Because VA patients may obtain approved health care outside the VA system during the study period, the cost of such care must be taken into account. We will use the Fee Basis file to capture all care provided outside the VA and paid for by VA.

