As described above, we will estimate the average cost of the intervention. For each participant, we will summarize their utilization and cost data. We will then perform a budget impact analysis of the intervention, comparing all health care costs for each arm of the study, including the costs of the intervention (e.g. providing the web-based BAI). Consistent with guidelines (Mauskopf et al., 2007), we will not include costs of developing the intervention or administrative overhead. Assuming also, that the BAI may impact both immediate decisions about alcohol use as well as decisions about other health care in the near future, we will analyze all health care utilization and costs incurred within the 12 months following randomization. We will also compare costs incurred in the first 6 months to those incurred in the second six months. We will estimate the budgetary impact for the two sites involved with the study. We will then extrapolate from these sites to create projections for other VAMCs based on the prevalence of patients with HCV and alcohol use at each site. This will allow us to estimate the budget impact of diffusing the web-based BAI throughout the VA system. Economics data will be managed in the same way as the clinical data and housed at HERC. We will adopt the same procedures and policies developed in the Aim 2.

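### The national budget projection carries a cost difference measured in patients with any liver disorder over to a count of HCV patients

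*Combined protocol and SAP*

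**What the plan says.** **Who supplies the costs.** Section 5.1 (Aim 2, Study Population) states "Veterans presenting to liver clinics who report engaging in any level of alcohol use within the prior 30 days will be recruited for the study" and continues "Additional criteria for inclusion include: (a) a liver disorder diagnosis, (b) not presently in treatment for a substance use disorder". Section 5.4 repeats this with liver disease in place of liver disorder. HCV is not required. Section 5.5 (Aim 3) says "OMHO will provide the project team with utilization data for patients included in the effectiveness study", and section 5.6 (Aim 3) says "For each participant, we will summarize their utilization and cost data" before comparing all health care costs between the arms over the 12 months after randomization.

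**Who is counted.** Section 5.6 (Aim 3) first estimates the budget impact at the two study sites. It then extrapolates to "create projections for other VAMCs based on the prevalence of patients with HCV and alcohol use at each site", in order to cost diffusion across the VA.

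**Who the projection is for.** Section 2.0 (Significance) speaks of implementation in HCV clinics nationwide. Section 5.1, in its opening and again under Aim 3, speaks of diffusion to Veterans with HCV.

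The text supplied does not restrict, stratify or reweight the costs by HCV status, and it states no uptake rate for the projection.

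**The concern.** A projection of this kind needs the per-patient cost difference and the patient count to describe the same people. Here they differ in two ways.

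- **Diagnosis.** The cost difference averages over all liver disorders; the count is of HCV. The documents give a reason why this could matter. Section 2.0 (Background and Rationale) describes drinking as a barrier to antiviral therapy in chronic HCV, and H2 in section 3.0 expects the intervention to improve antiviral eligibility. Any cost that follows from HCV antiviral treatment can arise only in HCV participants, and Aim 3 counts all health care costs.
- **SUD treatment.** Section 5.1 (Aim 3) expects the intervention to increase SUD treatment use in the first six months. Patients already in such treatment were excluded from the trial, so their cost difference was not measured, yet the count does not remove them.

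The VA partners would use the projection to judge the cost of a national rollout, so a total that mixes two populations could mislead that decision.

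**Working it through.** The documents give no unit cost, budget total, HCV share or uptake rate, so there is no Aim 3 figure to reproduce. The check below is algebra with assumed values.

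**Notation**

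- *h*: share of Aim 2 participants with HCV (not given)
- *c_H*, *c_N*: per-patient cost difference between arms, with and without HCV (not given)
- *r* = *c_N* / *c_H*
- *N_H*: count of patients with HCV who drink
- *u*: uptake of the intervention in routine care (not given)

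**Step 1: what the trial estimates.** *c_all* = *h c_H* + (1 − *h*) *c_N* = *c_H* [*h* + (1 − *h*) *r*].

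**Step 2: planned total against HCV target.** The plan gives no formula. Scaling a per-patient figure by patient numbers is the natural reading, so planned = *N_H* × *c_all*. The HCV target is *N_H* × *u* × *c_H*. The ratio is

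planned / target = [*h* + (1 − *h*) *r*] / *u*.

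**Step 3: population mix alone (*u* = 1).** The ratio equals 1 only when (1 − *h*)(*r* − 1) = 0, that is, when every participant has HCV or the cost difference does not depend on HCV. For assumed values:

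| *h* | *r* = 0.5 | *r* = 1 | *r* = 1.5 |
|---|---|---|---|
| 0.5 | 0.75 | 1.00 | 1.25 |
| 0.7 | 0.85 | 1.00 | 1.15 |
| 0.9 | 0.95 | 1.00 | 1.05 |

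For example, 0.5 + 0.5 × 1.5 = 1.25. The error can go either way. Because *c_H* and *c_N* are differences between arms, either could be near zero or negative, so *r* is not confined to this range.

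**Step 4: SUD treatment.** If a share *s* of the counted patients is already in SUD treatment, the count exceeds the population studied by a factor 1 / (1 − *s*). The documents do not give *s*.

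**Step 5: uptake (secondary).** With no uptake term, *u* = 1 is implied. At *r* = 1, assumed uptake of 0.8, 0.5 or 0.3 gives a ratio of 1/0.8 = 1.25, 1/0.5 = 2.0 or 1/0.3 = 3.3. Combined with the mix, the ratio runs from 0.75 (*h* = 0.5, *r* = 0.5, *u* = 1) to 1.25/0.3 = 4.17 (*h* = 0.5, *r* = 1.5, *u* = 0.3).

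**The case against.** The best defence is that the plan is under-specified here, not shown to be wrong. Section 5.6 speaks of extrapolating on the basis of prevalence and gives no formula, so both the multiplication and full uptake are inferences. That stands. The documents also mix HCV wording with liver-disorder wording (section 5.4 itself refers to HCV clinics beside a liver disease diagnosis). If nearly all participants turn out to have HCV, the mismatch in diagnosis is small. That stands too, but nothing in the plan ensures it.

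A reader might infer more than the documents support in three ways.

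- **That the direction of the error is known.** Step 3 shows it is not for an HCV target. For a target of all liver-clinic drinkers, and taking the same HCV share in the clinics as in the trial, the ratio is *h*/*u*. With *h* from 0.5 to 0.9 and *u* from 0.3 to 1, it runs from 0.50 to 3.00: the low count and the missing uptake term pull in opposite directions.
- **That the count is too small by the inverse of the HCV share.** That applies only if the target is all liver-clinic drinkers. Sections 2.0 and 5.1 name HCV, and the system-wide phrase in section 5.6 can be read as geographic reach. For an HCV target, an HCV count is the right kind of count; the cost mix and the SUD exclusion are what need attention.
- **That uptake would be about 80%.** Section 5.2 reports that another trial "currently has an 80% recruitment rate among eligible participants". That is consent to research in primary care, not use in routine liver care. Aim 2 enrolment is no better a guide, since participants are paid (section 5.2) and a coordinator guides them through the intervention (section 5.1).

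**Conclusion.** The point holds as a mismatch between the population in which costs are measured and the population counted. If section 5.6 is followed on its natural reading, the projection describes HCV patients only when the cost difference is the same with and without HCV or nearly all participants have HCV, and only when patients in SUD treatment are few or respond as the others do. The plan does not establish any of these.

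The size and direction of the error cannot be determined from the documents. The ranges above only illustrate it; the values of *h*, *r* and *u* are assumptions. The missing uptake range is a secondary gap.

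The two-site budget impact and the Aim 2 efficacy analysis are unaffected.

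**What to change.** In section 5.6 (Aim 3):

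1. **Name the target.** If it is HCV patients, estimate the per-patient cost difference in HCV participants, or report it by HCV status. If it is all liver-clinic drinkers, keep the all-participant estimate and scale by the count of that population.
2. **Align the count.** Remove patients in SUD treatment from the prevalence count, and state how the other Aim 2 exclusions (psychosis, dementia, terminal illness) are handled.
3. **Show uptake.** Present the projection over a stated, assumed range of uptake, and do not take research enrolment or the 80% recruitment rate as that range.

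**Cost.** No new patient assessments are needed, because section 5.5 lists liver disorder diagnosis among the assessment topics. The count needs a national extraction, which differs from the two-site recruitment search in section 5.2. The SUD utilization data that the Office of Mental Health Operations holds (section 5.5) may help, but the plan does not describe this step.

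**Downside.** The HCV-only estimate is less precise. With 170 per arm and equal cost variance, shares of 0.5, 0.7 and 0.9 leave 170 × *h* = 85, 119 and 153 HCV participants per arm, on average. The standard error grows by 1/√*h* = 1.41, 1.20 and 1.05. Randomization is stratified by site and alcohol dependence, not diagnosis, so the arms may be slightly unequal within HCV. Show the all-participant estimate beside the HCV estimate, both with intervals.

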5.7 Withdrawal of Subjects

Although we do not foresee any circumstances under which subjects will be withdrawn

from the research without their consent, there is the possibility that a participant may be deemed cognitively impaired, at which point we will withdraw them from the study. Withdrawing from the study at any point in time does not impact care or treatment at the VA.

6.1 Reporting

The Data Safety and Monitoring Plan will capture Serious Adverse Events (SAEs), i.e., death, hospitalization. It will also capture Adverse Events (AEs), i.e., suicidal or homicidal ideation, expression of severe distress, other serious psychiatric or medical symptoms. The Data Safety and Monitoring Plan will utilize the following categories in determining the severity of an event:

- A. Classification of Event Severity: Events will be labeled according to severity which is based on their impact on the patient. An Event will be termed 'mild' if it does not have a major impact on the patient, 'moderate' if it causes the patient some minor inconvenience, and 'severe' if it causes a substantial disruption to the patient's well-being.
- B. Event Attribution Scale: Events will be categorized according to the likelihood that they are related to the study intervention. Specifically, they will be labeled either definitely, probably, possibly, or unrelated to the study intervention.
- C. Expected Risks: This study includes no invasive procedures or medications. All changes to patients' treatment will be known to their liver care team.

We will use collected data to compare rates of SAEs between the control and intervention teams. Specifically, we will compare control and intervention serious adverse event rates and their attribution quarterly on three outcomes: Admissions for alcohol detoxification (with diagnoses), all other hospitalizations, and Deaths (with diagnosis).

In addition, we anticipate that we may encounter AEs in the following domains. These are described in greater detail below.

- (1) Breach of confidentiality associated with reporting suicidal or homicidal intent to appropriate authorities or health personnel
- (2) Severe distress as indicated by: (a) an increase of more than one standard deviation from their mean score on the PHQ-9 during follow-up assessments, (b) patient verbal report of a serious psychiatric distress at follow-up, (c) patients reporting significant distress due to the content of the self-report measures, or (d) patients reporting significant distress due to the content of the brief alcohol intervention. In each case, the research personnel will consult with the PI and Study Director to determine whether the participant's distress is significant enough to warrant an AE.
- (3) Suicidal ideation will be indicated by: (a) self-report of significant suicidal ideation on the PHQ-9, or (b) verbal report of thoughts of suicide. Even for those who report suicidal ideation on the PHQ-9, determination of suicidality will be based on a combination of the self-report information and the interaction between the research personnel and the participant. The research personnel will be trained to identify and address suicidal ideation in patients. If the patient articulates thoughts of death or suicidal ideation, the study team member will ask the patient to elaborate on recent suicidal thoughts/behavior (e.g., does the patient have a suicide

plan). The situation will be based on the patient's responses and whether the study team member perceives that the patient is in immediate danger (e.g., an active plan verbalized). Study personnel will follow established safety protocols and contact local licensed clinical staff when appropriate. Also, the study co-PIs [name] and [name] are well-suited to manage clinical situations involving the expression of intent to harm oneself as they are both licensed clinical psychologists in the State of California

(4) Homicidal ideation will be indicated by verbal report of thoughts of hurting others in general or harming a specific individual. The study does not directly ask about homicidal ideation but this information may be provided by a participant during an interaction with study team members. This protocol will be similar to that for suicidal ideation. Specifically, the research personnel will be trained to identify and address homicidal ideation in patients. If the patient articulates thoughts of hurting others, the study team member will ask the patient to elaborate on his/her thoughts/behaviors (e.g., does the patient have a plan or specific target?). The situation will be based on the patient's responses and whether the study team member perceives that the patient or someone else is in immediate danger. Study personnel will follow established safety protocols and contact local licensed clinical staff when appropriate. Also, the study co-PIs [name] and [name] are well-suited to manage clinical situations involving the expression of intent to harm another person as they are both licensed clinical psychologists in the State of California

(5) Given the study population, it is possible that participants will report other serious psychiatric or medical symptoms. Research staff will be trained to monitor significant abnormal behavior and/or report that the patient perceives him/herself to be in imminent need of medical treatment. If it is determined that the patient requires immediate care, the research staff will coordinate access to appropriate services.

Both [name] and [name] hold Ph.D.s in clinical psychology and have treated patients who have mental health and alcohol use disorders. In the event of other forms of medical care being the subject of a patient safety decision, [name] will seek the advice of Co-Investigator [name]., Chief of Hepatology at the VA Palo Alto, Co-Investigator [name]. of the San Francisco VA and/or consultant [name]. of the Palo Alto VA. All three physicians have extensive experience caring for Veterans who have liver disorders. These five project staff members will be available to consult with other project staff and/or to speak with the participant if any concerning events arise.

Triggers to action will be the participant's expression of severe distress, suicidal or homicidal ideation, and/or other serious psychiatric or medical symptoms. Research staff will be trained and prepared for situations in which a participant expresses severe distress. Specifically, all project staff will have been trained on VA's suicide risk assessment and response guidelines, including the capability of directly connecting suicidal participants to the 24-hour VA suicide hotline, as well as arranging with local psychiatry crisis management staff to assess and potentially hospitalize the patient. Subsequent to any participant's expression of severe distress, ideation, or other serious symptoms, project staff will make all reasonable attempts to re-contact the participant to monitor his or her well-being until the acute situation is resolved.

Research staff will also be trained and prepared for situations in which a participant not currently in addiction treatment reports severe alcohol misuse, e.g., a blackout, delirium tremens, alcohol-related injury). Such individuals will be protected by having project staff provide a referral to substance use disorder treatment at the VA closest to where they are residing. If the VA is rejected by the participant for any reason, project staff will utilize SAMHSA's (the federal agency within HHS that funds most non-VA substance use disorder

treatment) online substance abuse treatment facility locator to provide a referral.

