Our second aim is to implement a re-versioned web-based BAI in two liver clinics and to evaluate the implementability and effectiveness of this intervention to reduce alcohol consumption in Veterans with liver disorders at three- and six-months post treatment. To achieve Aim 2, we will conduct a randomized controlled trial utilizing a hybrid (Type 1) design with patient-level clinical outcome data and formative evaluation data collected (Curran et al., 2008). Participants will be randomized to one of two treatment conditions –(a) web-based BAI plus treatment-as-usual (TAU) or (b) TAU only. We will also conduct a formative evaluation to determine the feasibility and challenges of implementing the web-based BAI into liver clinics.

Method for Randomization

We plan to use a stratified permuted block design for randomizing participants where participants are stratified by site (Palo Alto or San Francisco) and baseline severity of alcohol use (alcohol dependent, not alcohol dependent). Four randomization strata will be used: not alcohol dependent (Palo Alto), alcohol dependent (Palo Alto), not alcohol dependent (San Francisco), and alcohol dependent (San Francisco). Within each stratum, we will construct blocks of consecutive patients that vary randomly in size (either 8 or 12 participants). Each block will contain equal quantities of assignments to the two study arms arranged (permuted) in random order. A random mixture of block sizes of 8 and 12 will be used to prevent forecasting

of treatment assignments by project personnel since neither the participants nor the project staff will not be blinded to the assigned treatment condition.

Web-Based BAI Content

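### Section 6.1: the mild and moderate grades overlap, and attribution is rated to an intervention that, on the natural reading, only one arm receives, so the attribution part of the quarterly comparison can lean only one way

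*Combined protocol and SAP*

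**What the plan says.** Section 6.1 (Reporting) sets up two scales and one comparison.

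- **Severity, item A.** For the two lower grades, an event is "termed 'mild' if it does not have a major impact on the patient, 'moderate' if it causes the patient some minor inconvenience". The top grade: "severe' if it causes a substantial disruption to the patient's well-being". No rule says which grade applies when an event meets two definitions.
- **Attribution, item B.** "Events will be categorized according to the likelihood that they are related to the study intervention", and "they will be labeled either definitely, probably, possibly, or unrelated to the study intervention". The scale has no category for study procedures such as the assessments.
- **Comparison.** The section first commits to comparing SAE rates between the control and intervention sides. It then adds: "we will compare control and intervention serious adverse event rates and their attribution quarterly on three outcomes". The three outcomes are admissions for alcohol detoxification, all other hospitalizations, and deaths.

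Section 5.1 (Aim 2) gives the arms as "a) web-based BAI plus treatment-as-usual (TAU) or (b) TAU only". Under Risks and Benefits for Aim 2 it says that TAU-only participants complete the assessment battery and receive a Patient Resource Sheet, which goes to both arms. They do not receive the BAI.

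**The concern.** A severity scale needs grades that do not overlap and that rise with impact. Here the definition of *mild* has only an upper limit, and that limit lies above the definition of *moderate*. Two people who follow the text faithfully can give the same event different grades.

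A comparison of attribution between arms is informative only if an event in either arm can receive any label. If the exposure being judged exists in one arm only, part of the difference is fixed before any event occurs. The more practical loss is that study-caused harm in the TAU arm has no label. Section 6.1 itself names distress due to the content of the self-report measures as a possible adverse event, and both arms complete those measures.

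At stake are the reliability of the mild/moderate split and the meaning of the attribution half of the quarterly comparison. The efficacy outcomes, the sample size and the SAE rates are not involved.

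**Working it through.** The point rests on no figure in the plan, so there is none to reproduce. It is checked by setting the definitions side by side.

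**Severity.** Take four levels of impact and ask which definitions each satisfies. The plan does not say how *major* relates to *substantial*. I take them as the same threshold.

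| Impact on the patient | Meets *mild*? | Meets *moderate*? | Meets *severe*? |
|---|---|---|---|
| None | yes | no | no |
| Minor inconvenience | yes | yes | no |
| More than a minor inconvenience, less than substantial | yes | no | no |
| Substantial disruption | no | no | yes |

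Row 2 shows that *moderate* lies wholly inside *mild*: 100% of events that meet the former meet the latter. This needs only that a minor inconvenience is not a major impact. Row 3 shows that an event worse than *moderate* falls back to *mild*. That result depends on the shared threshold. If *major* were set below *substantial*, events between the two would meet no definition. Row 4 shows that *severe* is separate from the lower grades.

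**Attribution.** Three things indicate what the study intervention is: the arms as defined in section 5.1, the contrast of control with intervention in section 6.1, and section 5.6 (Aim 3), which gives providing the web-based BAI as the example of the intervention's cost. On that reading:

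| Arm | Receives the BAI? | Labels that can apply |
|---|---|---|
| BAI plus TAU | yes | definitely, probably, possibly, unrelated (4) |
| TAU only | no | unrelated (1) |

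Let p be the share of an arm's SAEs labelled definitely, probably or possibly related. For TAU, p = 0 whatever the number of SAEs. For the BAI arm, p ≥ 0. Hence

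p(BAI) − p(TAU) = p(BAI) − 0 ≥ 0.

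The difference can be positive or zero, but never negative.

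This could arise in practice. Section 5.1 (Aim 3) hypothesises that the BAI will increase use of SUD treatment in the first 6 months, and detoxification admissions are one of the three compared outcomes. A rater could reasonably call such an admission possibly related in the BAI arm. The same admission in the TAU arm could not be given that label.

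**Shared procedures.** Suppose a participant in either arm is distressed by the questionnaires. The cause is the study but not the BAI, so the scale as written leads to *unrelated*.

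**The case against.** The case on the other side is substantial, and much of it stands as a limit on the point.

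- **The main safety comparison is already there and is sound.** Section 6.1 compares SAE rates by arm, and attribution is added to that comparison without restricting it. An imbalance that existed only in the labels would be seen beside the rates. This stands.
- **Severity drives nothing.** No severity count by arm is planned, and the triggers to action in section 6.1 (severe distress, suicidal or homicidal ideation, other serious symptoms) do not refer to the grade. This stands.
- **Assigning the highest grade met would remove the overlap.** It would, but the plan states no such rule, and the rule would not move the events in row 3 out of *mild*.
- **Study intervention is never formally defined.** Section 5.6, on mediators and moderators, once calls both arms intervention conditions. The satisfaction survey in section 5.5 treats provider education as something to be rated. Under that looser reading TAU events could be graded, so the zero for TAU is not a matter of definition. But the object being judged would then differ between arms and include usual clinic care, so it would still need to be stated.
- **A zero in an unexposed arm is transparent, and no decision rule uses it.** This is true, and it limits the harm. It also means that the comparison adds little to the rates.

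A reader might infer that raters will create a false signal or hide a real one because they know the arm. Section 5.1 indicates that project staff are unblinded, but section 6.1 does not say who rates attribution, and nothing in the documents shows bias in either direction. Rating from a summary with the arm removed would not be a general remedy. Distress due to the content of the BAI, which section 6.1 lists, reveals the arm, and a rater who does not know of the exposure cannot judge it as a cause.

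**Conclusion.** The point holds in a limited form. All events meeting *moderate* also meet *mild*, so that split is unreliable. With the study intervention read as the BAI, the TAU arm has one usable attribution label against four. The attribution part of the quarterly comparison can then show only a BAI-arm excess or no difference, and harm from procedures common to both arms cannot be labelled study-related.

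This rests on two assumptions. The first is that the study intervention means the BAI, which the wording favours but does not define. The second, needed only for the claim that the grades are out of order, is that *major* and *substantial* mark the same threshold.

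Two stronger readings are tempting, and the documents do not support them. One is that the severity grades carry no information; *severe* remains distinguishable. The other is that safety monitoring fails as a whole; the comparison of SAE rates does not depend on either scale. This is a correction that should be made, in proportion to a defect in the rules for labelling events.

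**What to change.** Revise section 6.1 as follows.

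1. **Severity.** Define three mutually exclusive, ordered grades: *mild*, at most a minor inconvenience; *moderate*, more than a minor inconvenience but no substantial disruption; *severe*, substantial disruption to well-being.
2. **Attribution.** Keep the four labels but apply them to two separate items. In both arms, rate relation to study procedures (the assessments and the resource sheet). In the BAI arm only, also rate relation to the BAI. Keeping the items apart preserves BAI-specific harm and gives both arms one item in common.
3. **Comparison.** State that the between-arm safety comparison rests on SAE rates regardless of attribution, and that attribution is listed descriptively.

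The cost is a few sentences in section 6.1 and one further attribution entry when an event is recorded in the BAI arm. It needs no extra staff and changes nothing in patient care, visits, sample size or the efficacy analysis.
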